6.2.15 Change from baseline

QMD Ref: Worldwide-TMP-ST-005-7.0 Effective: 12Aug2019	Governing QMD: Worldwide-SOP-ST-001
Confidentiality Statement	

This document is the property of Worldwide Clinical Trials Inc. and may not be duplicated, copied, altered or removed from company without prior approval from Worldwide Quality Assurance or in compliance with Worldwide Standard Operating Procedures.

Worldwide Clinical Trials Controlled Quality Management Document		
 WORLDWIDE CLINICAL TRIALS	Sponsor:	Helixmith Co., Ltd.
	Protocol Number:	VMALS-002-2
STATISTICAL ANALYSIS PLAN VERSION 3.0		

Change from baseline will be calculated as difference value on post-baseline visit – value on baseline visit. Percentage changes from baseline will be calculated as $100 * (\text{value on post-baseline visit} - \text{value on baseline visit}) / \text{value on baseline visit}$.

6.3 Conventions

All data listings, summaries, figures and statistical analyses will be generated using SAS version 9.4 or higher¹ unless otherwise noted.

Summaries will be presented by treatment group. Treatment group labels will be displayed as follows:

Engensis (N=XX)	Placebo (N=XX)	Overall (N=XX)
--------------------	-------------------	-------------------

Listings will be sorted in the following order: treatment group, Participant, parameter, visit or cycle unless otherwise stated. All data will be listed.

Continuous variables will be summarized by the number of non-missing observations, mean, 95% confidence interval for mean, median, standard deviation, and minimum and maximum.

Categorical variables will be summarized by presenting the frequency and percent. Percentages will be based on the number of non-missing observations or the participant population unless otherwise specified. For each variable, all categories will be shown. Zero frequencies (but not the percent) within a category will be presented.

6.3.1 Decimal Places

Decimal places for derived data described in section 6.2 will be determined by the scale of measurement unless otherwise stated. No decimal places will be displayed if the smallest calculated value is ≥ 100 ; 1 decimal place will be displayed when the smallest value is within the interval (10, 100), with 10 being inclusive; 2 decimal places will be displayed when the smallest value is within (1, 10), with 1 being inclusive; and so on for even smaller scales of measurement.

Derived data where it is known in advance the result will be an integer for example day, month, year, number of days and total scores (for rating scales) will be presented with zero decimal places.

Means, 95% confidence intervals for mean, medians and percentiles will be displayed to one more decimal place than the data, dispersion statistics (e.g. standard deviation) will have two more

QMD Ref: Worldwide-TMP-ST-005-7.0 Effective: 12Aug2019	Governing QMD: Worldwide-SOP-ST-001
Confidentiality Statement	

This document is the property of Worldwide Clinical Trials Inc. and may not be duplicated, copied, altered or removed from company without prior approval from Worldwide Quality Assurance or in compliance with Worldwide Standard Operating Procedures.

Worldwide Clinical Trials Controlled Quality Management Document		
 WORLDWIDE CLINICAL TRIALS	Sponsor:	Helixmith Co., Ltd.
	Protocol Number:	VMALS-002-2
STATISTICAL ANALYSIS PLAN VERSION 3.0		

decimal places, and the minimum and maximum will be displayed to the same number of decimal places as reported in the raw data. Percentages will be displayed with one decimal place.

Rounding will be carried out according to the following rules: if the digits on the right start with 0, 1, 2, 3 or 4, then the rounding digit will remain unchanged, if the digits on the right begin with 5, 6, 7, 8 or 9, then the rounding digit will be increased by 1.

6.4 Participant Disposition

The following data will be tabulated: number of screened participants, screen failures, participants in the Safety Analysis Population and cases of withdrawal/discontinuation by primary reason (Table 14.1.1.1). Participant visits will be presented in a separate table (Table 14.1.1.2).

The following data will be presented in a listing (Listing 16.2.1.1):

- Date of Informed Consent
- Original Consented Protocol Version
- Date of Discontinuation
- Primary reason for discontinuation
- Study completion (Yes/No)
- Date of last dose
- Date of last visit

6.5 Protocol Deviations

A listing of protocol deviations will be provided. The listing will include participant number, protocol deviation description and deviation comments (Listing 16.2.1.2).

6.6 Baseline Comparability

Demographics and baseline characteristics will be presented for the Safety Analysis Population.

The comparability of treatment groups with respect to participant demographics and baseline characteristics will be assessed in a descriptive manner, but no formal statistical testing will be performed.

Standard continuous or categorical variable summaries will be presented by randomized treatment group for the following variables:

- Demographic and Baseline Characteristics (Table 14.1.2.1)
 - Age

QMD Ref: Worldwide-TMP-ST-005-7.0 Effective: 12Aug2019	Governing QMD: Worldwide-SOP-ST-001
Confidentiality Statement	

This document is the property of Worldwide Clinical Trials Inc. and may not be duplicated, copied, altered or removed from company without prior approval from Worldwide Quality Assurance or in compliance with Worldwide Standard Operating Procedures.

Worldwide Clinical Trials Controlled Quality Management Document		
 WORLDWIDE CLINICAL TRIALS	Sponsor:	Helixmith Co., Ltd.
	Protocol Number:	VMALS-002-2
STATISTICAL ANALYSIS PLAN VERSION 3.0		

- Gender
- Child-bearing potential
- Race
- Ethnicity
- Weight
- Height
- BMI

All demographic and baseline characteristics, including also Coagulation Profile and Viral Screening will be presented in listings (Listings 16.2.4.1 - 16.2.4.4).

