## 2.2. **Background**

### 2.2.1. **Pathophysiology of Amyotrophic Lateral Sclerosis**

Amyotrophic Lateral Sclerosis (ALS) is an adult-onset neurodegenerative disorder characterized by the loss of upper and lower motor neurons. The disease is diverse in its presentation, cause, and progression, but, in general, ALS presents clinically as asymmetric muscle weakness, wasting, spasticity, weight loss, dysphagia, and paralysis; in 10% to 15% of patients, cognitive impairment may arise before or following that of motor neuron dysfunction. Pathologically, ALS is characterized by progressive degeneration and loss of motor neurons in the spinal cord, brainstem, and cerebral cortex. From the time of diagnosis, median survival is 3 to 5 years; about 10% of patients can survive for  $\geq 10$  years. While the majority of ALS cases are sporadic (primary or idiopathic), about 5% to 10% of patients have a positive family history (familial ALS), with a mutation in the Cu/Zn superoxide dismutase 1 (SOD1) gene accounting for 10% of familial ALS.

Estimates of the incidence of ALS worldwide range from 1 to 3 cases per 100,000 people annually, with a higher incidence in Caucasians, in people who smoke, and in several geographic regions in which environmental toxins are suspected. The ALS Association, the Centers for Disease Control and Prevention, and the National Institute of Neurological Disorders and Stroke estimate that as many as 30,000 Americans may have the disease at any given time, with approximately 5,600 newly diagnosed patients annually.a

a <http://www.alsa.org/about-als/who-gets-als.html> (accessed October 12, 2015);  
<http://www.cdc.gov/als/WhatisALS.aspx> (accessed October 12, 2015);  
[http://www.ninds.nih.gov/disorders/amyotrophicsclerosis/detail\\_ALS.htm](http://www.ninds.nih.gov/disorders/amyotrophicsclerosis/detail_ALS.htm) (accessed October 12, 2015)

undergo transcriptional dysregulation and abnormal ribonucleic acid (RNA) processing which,

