## 4. STUDY DESIGN

### 4.1. Overall Design

VMALS-002-2 is a Phase 2a, double-blind, randomized, placebo-controlled, multicenter study designed to assess the safety of IM administration of Engensis in Participants with ALS as compared to Placebo. Study Participants will be randomized in a 2:1 ratio to Engensis or Placebo (control group). The study will include only patients with limb onset of ALS.

**Screening.** Screening activities (see SoA, Section 1.3) include assessments to determine study eligibility, assessments to establish Baseline results for use in analysis of endpoints, and Baseline safety assessments. All Screening activities will occur within the 30 days prior to Day 0.

**Randomization.** Participants who meet the eligibility criteria will be randomly assigned in a 2:1 ratio to one of the two treatment arms, Engensis or Placebo. Randomized treatment assignment will occur through the EDC randomization module in a double-blinded fashion. Blinding will be achieved by having the study medication (Engensis and Placebo) prepared by the unblinded Pharmacist or delegated staff.

**Treatment Period.** Participants will undergo three Treatment Cycles of Study Injections (Engensis or Placebo) at 60-day intervals (on Days 0 and 14, Days 60 and 74, and Days 120 and 134), with follow-up Visits at Days 30, 84, 144, and 180/ET.

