### 5.1. Inclusion Criteria

1. Male or female Participants age  $\geq$  18 years, but  $\leq$  80 years, at time of completion of the informed consent process
2. Clinically definite or probable Amyotrophic Lateral Sclerosis (ALS) or laboratory-supported probable ALS as defined in the revised El Escorial/Airlie House diagnostic criteria
3. The site of onset of ALS symptoms is a limb and experiencing symptoms of lower motor dysfunction (e.g., weakness, atrophy, cramps, poor circulation, etc.) with upper motor neuron symptoms (e.g., brisk reflexes, spasticity)
4. Onset of ALS symptoms  $\leq$  4 years
5. Slow Vital Capacity (SVC)  $\geq$  50% of predicted value at Screening
6. Not taking riluzole, or on a stable dose (defined as no noted toxicities) for at least 30 days prior to Screening and throughout the study
7. Not taking edaravone or on a maintenance cycle for at least 30 days prior to Screening and throughout the study
8. For females of childbearing potential, a negative urine pregnancy test at Screening and on Day 0
9. Male Participants and their female partners must agree to use double-barrier contraception during the study or provide proof of postmenopausal state (minimum 1 year) or surgical sterility
10. Male Participants must not donate sperm during the study
11. Female Participants must be nonpregnant, nonlactating, and either postmenopausal for at least 1 year, or surgically sterile for at least 3 months, or agree to use double-barrier contraception from 28 days prior to randomization (Day 0) and/or their last confirmed menstrual period prior to study randomization (whichever is longer) until the end of the study
12. Capable of complying and willing to comply with the requirements and restrictions in the informed consent form and this protocol
13. Willing to forgo new experimental ALS treatments for at least 6 months following randomization

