### **5.3. Number of Participants**

The target sample size is 18 Participants who will be randomized in a 2:1 ratio to Engensis or Placebo (12:6).

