3.2 Exploratory Endpoints

- Change from Baseline (Day 0) in total mean Revised Amyotrophic Lateral Sclerosis Function Rating (ALSFRS-R) scores at Day 180 for Engensis compared to Placebo
- Change from Baseline (Day 0) in ALSFRS-R subscores for Fine and Gross Motor Functions (sum of scores for items 4 to 9) and for Bulbar Function (sum of scores for items 1 to 3) on Days 30, 60, 84, 120, 144, and 180 for Engensis compared to Placebo
- Changes in the slope of the total ALSFRS-R score over time for Engensis compared to Placebo
- Change from Baseline (Day 0) in muscle strength assessed bilaterally by Handheld Dynamometry (HHD) in muscles in the upper and lower extremities on Days 30, 60, 84, 120, 144, and 180 for Engensis compared to Placebo
- Change from Baseline (Day 0) in the Accurate Test of Limb Isometric Strength (ATLIS) where available at Days 30, 60, 84, 120, 144, and 180 for Engensis compared to Placebo
- Change from Baseline (Day 0) in Quality of Life (QoL) using the ALS Assessment Questionnaire (ALSAQ; with 40 items, ALSAQ-40) on Days 84 and 180 for Engensis compared to Placebo
- Patient Global Impression of Change (PGIC) and Clinical Global Impression of Change (CGIC) at Days 84 and 180 for Engensis compared to Placebo
- Change from Baseline (Day 0) in Slow Vital Capacity (SVC) on Days 30, 60, 84, 120, 144, and 180 for Engensis compared to Placebo
- Time to tracheostomy for Engensis compared to Placebo
- Time to all-cause mortality by Day 180 for Engensis compared to Placebo

QMD Ref: Worldwide-TMP-ST-005-7.0 Effective: 12Aug2019	Governing QMD: Worldwide-SOP-ST-001
Confidentiality Statement	

This document is the property of Worldwide Clinical Trials Inc. and may not be duplicated, copied, altered or removed from company without prior approval from Worldwide Quality Assurance or in compliance with Worldwide Standard Operating Procedures.

Worldwide Clinical Trials Controlled Quality Management Document		
 WORLDWIDE CLINICAL TRIALS	Sponsor:	Helixmith Co., Ltd.
	Protocol Number:	VMALS-002-2
STATISTICAL ANALYSIS PLAN VERSION 3.0		

- Change from Baseline (Day 0) in biomarkers for muscle atrophy in biopsies collected before and after injections for Engensis compared to Placebo

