4 SAMPLE SIZE

A sample size of 18 Participants was chosen for safety assessments and preliminary evaluation of exploratory endpoints.

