6.2.3 Duration / Study Day / Time

Study day will be calculated as the number of days from first Study Injection.

- date of event – date of first Study Injection + 1, for events on or after first Study Injection
- date of event – date of first Study Injection, for events before first Study Injection

Duration of ALS diagnosis will be presented in months and calculated as (Date of Screening – Date of Onset of Symptoms) / 30.4375.

Time to tracheostomy will be calculated as time from date of first Study Injection to date of first occurrence of ALSFRS-R questionnaire with answer “**0 - Invasive mechanical ventilation by intubation or tracheostomy**” to question “**12. Respiratory insufficiency**” presented in days.

Time to all-cause mortality will be calculated as period from date of first Study Drug Injection to date of death within 180 days presented in days.

Both time-to-event endpoints will be censored by date of last visit.

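### ALSFRS-R change and slope are compared between 12 Engensis and 6 Placebo participants without deriving, tabulating or adjusting for pre-study rate of decline, so a chance imbalance in progression would not be visible

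*SAP*

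**What the plan says.** **Endpoint and analysis.** SAP 3.2 lists as exploratory "Changes in the slope of the total ALSFRS-R score over time for Engensis compared to Placebo", together with change in total score at Day 180 and subscore changes by visit. SAP 6.15.1 summarises scores and changes by visit and arm (Table 14.6.1) and shows slope only as a plot of values by visit. Under SAP 6.3 each arm's mean gets a 95% CI. No slope estimate, between-arm difference or interval for a difference is planned.

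**Size.** Protocol 5.3 sets 18 participants, split 12:6. SAP 4 gives the basis: "A sample size of 18 Participants was chosen for safety assessments and preliminary evaluation of exploratory endpoints". SAP 6.11 marks efficacy analyses as not applicable.

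**Who enters.** Protocol 2.2.1 says of ALS: "The disease is diverse in its presentation, cause, and progression". Inclusion criterion 4 in Protocol 5.1 limits "onset of ALS symptoms" to 4 years or less, and criterion 5 requires SVC of at least 50% predicted. Protocol 4.1 adds: "The study will include only patients with limb onset of ALS". Neither eligibility list has a criterion on rate of decline or on ALSFRS-R. Screening lasts up to 30 days and there is no run-in. Protocol 4.5, 5.4.2 and 6.3.1 and SAP 5 name no stratification factor.

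**Baseline description.** SAP 6.6 states: "The comparability of treatment groups with respect to participant demographics and baseline characteristics will be assessed in a descriptive manner". Its variables are age, gender, child-bearing potential, race, ethnicity, weight, height and BMI. SAP 6.7 adds an ALS History table: diagnosis category, site of onset, and lower and upper motor neuron symptoms. SAP 6.2.3 says "Duration of ALS diagnosis will be presented in months" and computes this from symptom onset to Screening, but no table is named for it. SAP 6.2.2 defines baseline as the last single value before injection, which is a level and not a rate.

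**The concern.** For change or slope over 180 days, how fast each participant was declining before entry is the natural baseline reference. The protocol's own background points the same way: Protocol 2.2.2 reports that the edaravone result reached significance only in participants diagnosed less than two years earlier and progressing rapidly. Here the rate needs no new data, since onset date and Day 0 score are both recorded, yet the two are never combined.

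With six Placebo participants, the arms can easily differ by chance in their mix of fast and slow progressors. A reader of the ALSFRS-R plot could not tell such a difference from a drug effect, in either direction. The risk of over-reading is concrete: Protocol 2.1 reads a plateau in the open-label ALS study as suggesting slower progression, and Protocol 2.3.2 looks ahead to a durable therapeutic effect if outcomes are favorable. SAP 6 allows further analyses if the data warrant them, but a pre-study rate introduced after the curves are seen would carry little weight.

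**Working it through.** **Plan's own figure.** 18 × 2/3 = 12 and 18 × 1/3 = 6, so the split reproduces. The total of 18 cannot be reproduced, because no alpha, power, effect size or SD is given.

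**Chance imbalance at 12:6.** For any covariate with SD s, the SD of the arm difference in means is s × √(1/12 + 1/6) = s × √0.25 = 0.5 s.

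**What that means for slope with no drug effect.** The documents give no SD of slope. Assume it is CV × mean decline, with CV from 0.5 to 1.0. The SD of the arm difference, as a fraction of mean decline, is then 0.5 × CV. The benchmark is the 33% reduction that Protocol 2.2.2 quotes for edaravone.

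| CV (assumed) | SD of difference | 95% chance range | P(Engensis looks ≥33% slower) |
|---|---|---|---|
| 0.5 | 0.25 | ±0.49 | 1 − Φ(0.33/0.25) = 9.3% |
| 0.75 | 0.375 | ±0.73 | 1 − Φ(0.33/0.375) = 18.9% |
| 1.0 | 0.50 | ±0.98 | 1 − Φ(0.33/0.50) = 25.5% |

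The same probabilities apply to Engensis looking at least 33% faster. They cover all chance variation in slope; the pre-study rate accounts for only part of it.

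**A count version.** If 8 of 18 are fast progressors (assumed), the number falling in the 6 Placebo places is hypergeometric with C(18,6) = 18,564 possible draws. P(4 or more) = (3,150 + 560 + 28)/18,564 = 20.1%. P(1 or fewer) = (210 + 2,016)/18,564 = 12.0%.

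**Why separate summaries do not show the rate.** Take two participants with Day 0 scores 24 and 42 and durations 12 and 48 months (illustrative).

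- Paired (24, 12) and (42, 48): rates (48 − 24)/12 = 2.0 and (48 − 42)/48 = 0.125, mean 1.06 points per month.
- Paired (24, 48) and (42, 12): rates 24/48 = 0.5 and 6/12 = 0.5, mean 0.5.

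Every summary of score and of duration is identical, yet the mean rate differs about twofold.

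**What adjustment would gain.** Let r be the correlation of pre-study with on-study slope (assumed; the documents give none). With one covariate and two arms totalling 18, the SD of the adjusted difference is the raw SD × √[(1 − r²)(1 + 1/14)].

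| r (assumed) | Adjusted SD / raw SD | Simulated SD, CV 0.5 (raw 0.25) | P(≥33% slower), CV 0.5 | P(≥33% slower), CV 1.0 |
|---|---|---|---|---|
| 0.3 | √(0.91 × 15/14) = 0.987 | 0.245 | 8.8% | 25.5% |
| 0.5 | √(0.75 × 15/14) = 0.896 | 0.224 | 6.8% | 23.2% |
| 0.7 | √(0.51 × 15/14) = 0.739 | 0.185 | 3.7% | 18.3% |

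The last three columns come from 40,000 simulated trials. By simulation the SD falls by about 2%, 10% and 26%; the formula gives 1.3%, 10.4% and 26.1%.

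**Why not subtract.** With equal SDs, on-study minus pre-study rate multiplies the SD by √[2(1 − r)]: 1.18 at r = 0.3, 1.00 at r = 0.5 and 0.77 at r = 0.7. The Day 0 score also enters both (48 − Day 0)/months and (Day 0 − Day 180)/6, with opposite signs, so its measurement error is amplified.

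**The case against.** The best reply is that this is a small Phase 2a safety trial. The slope is exploratory, shown as a graph and untested, so no formal type I error is at stake, and a descriptive baseline comparison without tests is accepted practice. All of that stands, and it limits the point to how an exploratory figure can be read.

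A reader might also infer stronger things that the documents do not support.

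- *That the comparison is biased, or that eligibility, the lack of a run-in or unstratified allocation is an error.* Randomization keeps the comparison unbiased in expectation, and limb onset and the SVC floor narrow the mix somewhat. In simulation, stratifying at the median pre-study rate lowered the SD of the difference by only about 3% to 17% over the same range of r.
- *That nothing in the plan bears on disease status at baseline.* Day 0 ALSFRS-R is tabulated by arm in Table 14.6.1, SVC by visit and arm in Table 14.6.7, and ALS history in Table 14.1.3.1. Months since onset is to be presented, and SAP 6.3 promises that all data will be listed. What is missing is the ratio, per participant.
- *That a 33% false slowing is the expected result.* One can construct it: two participants scoring 36 at Day 0, with onset 12 and 48 months earlier, decline at 12/12 = 1.0 and 12/48 = 0.25 point per month, or 6.0 and 1.5 points over 180 days. With 4 of 6 fast on Placebo and 4 of 12 on Engensis, mean losses are (4 × 6 + 2 × 1.5)/6 = 4.5 and (4 × 6 + 8 × 1.5)/12 = 3.0. This needs two extreme rates, 8 fast progressors among 18, and rates that persist perfectly. The documents support none of these.

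**Conclusion.** The point holds as a cheap improvement to the exploratory analysis. Pre-study rate is nowhere derived, tabulated or adjusted for, and at 12:6 an imbalance of 0.5 covariate SD is an ordinary chance event. Such an imbalance could mimic or hide an effect on ALSFRS-R without showing in any planned table. The 9.3% to 25.5% chance of an apparent slowing of at least 33% rests on the assumed CV of 0.5 to 1.0 and approximate normality; the 0.5 factor rests on nothing but the split. The value of tabulating the rate does not depend on r. The value of adjusting for it does, and at r = 0.3 it is close to nil. Neither step lets 18 participants separate a plausible effect from chance.

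**What to change.** Specify the following before database lock:

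1. In SAP 6.2.10, derive pre-study rate = (48 − Day 0 ALSFRS-R total) / (months from symptom onset to Day 0). The duration in SAP 6.2.3 stops at Screening, so the Day 0 endpoint needs its own line.
2. Tabulate this rate by arm, with months since onset and Day 0 ALSFRS-R, in Table 14.1.2.1 or the ALS History table 14.1.3.1.
3. In SAP 6.15.1, beside the raw summaries, report the between-arm difference in on-study slope (or in Day 180 change) with a 95% CI, with pre-study rate as a covariate and not subtracted. State that the estimate is descriptive.

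The cost is one derived variable, three table rows and one model, with no new data or visits. The adjustment spends one degree of freedom.

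Onset dates may be imprecise. SAP 6.2.7 covers diagnosis dates only, and extending its 1 January rule to year-only onset dates could lengthen duration by about 11 months. For a Day 0 score of 36 and a true onset in December, 12 months before, the rate would read 12/23 = 0.52 instead of 12/12 = 1.0 point per month. The SAP should state the rule for partial onset dates and flag the participants it affects.
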